11.3.5 PET/MR (PART B)

PET scan 3: The subject inhales (1-2 puffs) for about 3-5 seconds to receive about 12 µL solution corresponding to approximately 50 MBq [¹¹C]nicotine. A dynamic PET scan is performed over the brain 0-30 min. Arterial blood is collected as discrete samples of 5 mL each, taken at 2, 4, 6, 8, 10, 15, 20 and 30 minutes to determine radioactivity in whole blood.

Optional – extended brain uptake study

If the results from PET-scan 3 show significant, quantifiable, uptake of radioactivity in the brain, the study is extended to include 3 more subjects, to a total of 5 individuals receiving the formulation that shows the best uptake.

For the brain scans, the dynamic PET data is acquired in list mode, and will initially be reconstructed into 6 x 10s, 3 x 20s, 2 x 30s, 2 x 60s, 2 x 150s and 4x 300s frames. The scanner will be started 30 seconds before the tracer administration. The data collected 30s before inhalation will not be reconstructed. The registration of data is depending on the resulting images, the frame definition may be optimised, taking the inhalation protocol into account.

11.3.5.1 *MR-scan for anatomical localisation of [¹¹C]nicotine uptake:*

All subjects participating in PART B will perform an MRI at any suitable timepoint during the study period (after screening until end-of-study- visit). With MRI, a standard structural T1-weighthed volume is acquired to be used for anatomical localisation of [¹¹C]nicotine uptake in combination with PET scans acquired.

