6 INTRODUCTION

6.1 Background

E-cigarettes have become a popular alternative to cigarette smoking and are garnering significant attention as potentially reduced exposure products and smoking cessation products. E-cigarettes consist of a battery, heating component, and a reservoir (often referred to as a pod, cartridge, or tank) containing tobacco-derived nicotine in a solution composed of glycerine and/or propylene glycol and flavourings. Upon activation, the heating element heats the solution and the consumer inhales the resulting vapour.

E-liquid formulations aim to provide smokers with an experience that would allow for maximal displacement of combustible cigarettes while at the same time not serving as a gateway to other more toxic products for non-smokers. Key elements that contribute to an acceptable initiating experience include the nicotine content in the products as well as the response that consumers have in terms of satisfaction and prevention of symptoms of withdrawal. One commercially successful development in e-liquid formulations is the use of nicotine salts, which reproduce a form of nicotine naturally available in the tobacco leaf and are able to provide higher levels of nicotine delivery.

6.1.1 *myblu*TM e-cigarette system

*myblu*TM is a commercially available, two-piece, closed e-cigarette system comprised of a rechargeable 350 milliampere hour (mAh) battery and a disposable pod. The pods connect directly and contain the mouthpiece, heating element, are pre-filled with e-liquid, and are compatible only with *myblu*TM batteries. During use, a consumer inhales through the mouthpiece and a sensor in the battery detects the change in air pressure which activates the heating element. The e-liquid heats to an aerosol which the consumer inhales.

The battery is charged with a micro-USB charger and produces a typical output of 3.7 Volt (V) (maximum 3.9 V). Under typical usage conditions, the pods would contain 1.5 millilitre (mL) of e-liquid which lasts approximately 200 puffs, depending on individual use behaviours. Each e-liquid contains a mixture of glycerine, propylene glycol, nicotine freebase, and a proprietary blend of flavours.

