Radioactively labelled nicotine will be given to the study subjects. The amount of radioactivity expected in the device is estimated to be about 200 MBq at the time of administration. Approximately up to 25 MBq is administered to the subject by two 3-5 second inhalations, as 1-2 consecutive puffs withdrawn from the device for each tracer administration. The effective dose of 50 MBq (2 inhalation administrations) of [¹¹C]nicotine is not likely to exceed 0.2 millisievert (mSv).

The effective dose in radiation protection and radiology is a measure of the cancer risk to a whole organism due to ionising radiation delivered non-uniformly to part(s) of its body. It takes into account both the type of radiation and the nature of each organ being irradiated. Additionally, the Ultra Low Dose Computed Tomography (ULDCT) used for attenuation correction and for anatomical orientation, will give a radiation dose of approximately 0.28 mSv for the entire study. For subjects participating in Part B (Brain scan only) the dose from ULDCT is 0.05 mSv per investigation.

The total radiation dose to the subjects participating in this study with two positron emission tomography/computerised tomography (PET/CT) investigations and two inhalations of [¹¹C]-labelled nicotine will thus be less than 1.0 mSv (0.5 mSv for part A and 0.3 mSv for part B). This dose falls within Category I that allows up to 1 mSv for subjects with an age above 50 years. This dose limit relies on the guideline: “European commission Radiation protection 99, Guidance on medical exposures in medical and biomedical research. 1998 Directorate-General Environment, Nuclear Safety and Civil protection”.

To our knowledge, there are no publications reporting effective dose due to [¹¹C]nicotine inhalation or intravenous injection. The Swedish Radiation Safety Authority states an effective dose of 0.004 mSv/MBq for intravenous injection of neuroreceptor ligands, compared to 0.003 mSv/MBq for ¹¹CO inhalation. Homogeneous distribution of a [¹¹C]-labelled tracer results in 0.003 mSv/MBq as well. Based on this data, the effective dose of 50 MBq [¹¹C]nicotine inhalation is not likely to exceed 0.004 mSv/MBq, or 0.2 mSv.

Bergström et al, [1] reported 45% of administered nicotine vapour in the oral cavity at end of inhalation, and 8% at 45 minutes past inhalation. Assuming that 50% of the inhaled activity (25 MBq) remains on the mucosa of the oral cavity, with an effective half life of ten minutes,

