Each subject is expected to participate in the study for approximately 7 days from the day of PET-sessions (Day 1, Visit 2) to the End-of Study Visit. The Screening Visit will be performed within 28 days prior to PET-scanning (Day -28 to Day -1).

The schedule of events is shown in Table 8.1-1.

Study assessments are described in Section 11.

Table 8.1-1 Schedule of events PART A

Visit	Refer to CSP section:	Visit 1 Screening	Visit 2 ⁰					Visit 3 End-of- study
			Day -28 to Day -1	Admission 08:00	10:00	12:00	14:00	
Assessment/ Approximate timepoints								Phone call Day 7 (±2) ²
Informed Consent	14.3	X						
Inclusion/exclusion criteria	9.4, 9.5	X		X ³				
Demographics	11.2	X						
Medical/surgical history	11.2.5	X						
HIV, hepatitis B and C	11.2.7	X						
Alcohol breath test	11.2.9	X		X				
Urine Drug Screen	11.2.8	X		X				
Weight/height (Body Mass Index [BMI])	11.2.4	X						
Physical Examination	11.2.12	X						
Clinical Laboratory Profile	11.2.11	X						
Vital Signs	11.4.3	X						X
12-lead ECG	11.2.13	X						
Inhalation training	11.3.1	X		(X)				
Modified Allen test	11.3.2	X		X				
Insertion of arterial catheter	11.3.2			X				
PET assessment ⁴	11.2.11				X			X
Sampling arterial blood for radioactivity assessment ⁴	11.2.11				X			X
IP administration ⁴	10.5				X			X
Meals at the research clinic	9.6			X			X	
Removal of arterial catheter	11.3.2							X
Discharge from research clinic								X
Baseline symptoms	11.2.10	X		X				
Adverse events	11.4.2							----- X -----
Prior and concomitant medications	11.2.6							----- X -----

CSP= Clinical Study Protocol, HIV= Human Immunodeficiency Virus, ECG= Electrocardiogram

1. Timepoints given for Visit 2 are approximate and may be adjusted over the day if needed for logistical reasons in agreement between the research clinic and the PET-Centre.
2. Or after early withdrawal.
3. Confirmation of eligibility.
4. Activities performed at the PET-Centre

8.1.2 **PART B: PET 3**

In PART B of the study, two different formulations of [¹¹C]nicotine will each be given to 2 subjects. The subjects will have one PET-assessments each (PET 3) after two inhalations of [¹¹C]nicotine via the *myblu*™.

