PART B will be completed for 2 subjects on each formulation before a decision will be taken if 3 additional subjects should be added to PART B. The decision is based on whether the results from the first scans show significant, quantifiable uptake of radioactivity in the brain. If 3 additional subjects are included, they will be treated with the formulation that showed the best uptake profile.

The IP will be given as inhalation (“puffs”) via the *myblu*™ e-cigarette system to obtain a tracer dose of up to 50 MBq.

Subjects will come for 2 visits to the clinic, 1 MRI assessment visit (if not on the PET assessment day) and have 1 End-of Study follow-up telephone call (Visit 3).

Screening (Visit 1) will take place from Day -28 to Day -1 and will include an eligibility check, review of health status and inhalation training, see Table 8.1-2 for details.

At Visit 2, subjects will arrive to the clinic in the morning of Day 1 and will remain at the clinic until the afternoon. Day 1 will contain pre-PET safety assessment, preparation for the PET assessments (including insertion of an arterial catheter), one PET assessment session and safety follow-up (including removal of arterial catheter) after the PET assessment.

The subjects will have breakfast (optional) at the research clinic before the PET-session. Lunch (optional) will be served at the research clinic after the PET session.

The subjects will be carefully monitored by clinical staff during and after the PET-session. There is immediate access to equipment and qualified staff in case of emergency.

A final End-of-Study phone call (Visit 3) will take place on Day 7 (± 2) or after early withdrawal to follow up on safety (AEs and concomitant medications).

During the study period, the subjects will also have an MRI-scan. The MRI can be performed at any suitable timepoint during the study after the screening visit until the End-of-Study-visit.

Each subject is expected to participate in the study for approximately 7 days from the day of PET-session (Day 1, Visit 2) to the End-of Study Visit. The Screening Visit will be performed within 28 days prior to PET-scanning (Day -28 to Day -1).

The schedule of events is shown in Table 8.1-2.

Study assessments are described in Section 11.

Table 8.1-2 Schedule of events PART B

Visit	Refer to CSP section:	Visit 1 Screening	Visit 2 ¹			Visit 3 End-of- study
			Day -28 to Day -1	Admission 08:00	Day 1	
Assessment/ Approximate timepoints						Phone call

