10.5 Treatment administration

Instructions on the proper use of the *myblu*™ products will be provided prior to use. Product use in the study sessions will consist of 1-2 puffs of each 3-5 seconds, followed by an inhalation of the vapour into the lungs.

Inhalation training of study subjects, see 11.3.1.

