11.3.4 PET/CT (PART A)

Administration/inhalation and subject preparation

The subject will be moved from the research site to the PET-Centre approximately 30 minutes before the PET-scan.

The subject is positioned in the PET-CT camera and a ULDCT scan is performed to correct for attenuation of the photons and to outline the anatomy. In supine position the subject inhale from the device, without changing the head or body position. The PET-CT operator takes the inhalation device and the PET-scan begins.

The inhalation device is measured before and after inhalation to determine total amount of [¹¹C]nicotine delivered to the subject. The amount of [¹¹C]nicotine lost when the subject exhales cannot be determined.

PET-protocol

PET-scan 1: The subject inhales (1-2 puffs) for about 3-5 seconds to receive about 10-24 µL solution corresponding to approximately 25 MBq [¹¹C]nicotine. A dynamic 40 min PET scan is performed with the oral cavity/throat and large bronchi in field-of-view (20 cm). Arterial blood is collected as discrete samples of 5 mL each, taken at 2, 4, 6, 8, 10, 15, 20 and 30 minutes to determine radioactivity in whole blood.

PET-scan 2: The subject inhales (1-2 puffs) for about 3-5 seconds to receive about 10-24 µL solution corresponding to approximately 25 MBq [¹¹C]nicotine. A dynamic 40 min PET scan is performed with part of the lung in field-of-view (20 cm). Arterial blood is collected as discrete samples of 5 mL each, taken at 2, 4, 6, 8, 10, 15, 20 and 30 minutes to determine radioactivity in whole blood.

For both lung and oral cavity scans, the dynamic PET data is acquired in list mode, and will initially be reconstructed into 6 x 10s, 3 x 20s, 2 x 30s, 2 x 60s, 2 x 150s and 6 x 300s frames. The scanner will be started 30 seconds before the tracer administration. The data collected 30 seconds before inhalation will not be reconstructed. The registration of data is depending on the resulting images, the frame definition may be optimised, taking the inhalation protocol into account. The static scans over lung and oral cavity will be acquired as single frame scans of 600s.

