11.4.2.13 Treatment of overdose

An overdose is a dose in excess of the dose specified for each cohort in this clinical study protocol (CSP).

Over-dosing is not likely to occur in this study since all IP will be administered by site personnel under medical surveillance. In cases of accidental overdose, standard supportive measures should be adopted as required.

An overdose should be documented as follows:

- An overdose with associated AE is recorded as the AE diagnosis/symptoms in the AE Log of the eCRF.
- An overdose without associated symptoms is only reported in the subject's medical records.

11.4.3 *Vital signs*

Systolic and diastolic blood pressure and pulse will be measured in supine position after 10 minutes of rest.

Vital signs will be judged as normal, abnormal, not clinically significant or abnormal, clinically significant. The assessment will be recorded in the eCRF.

Post-IP vital signs, where the change from the values measured at the screening visit is judged as “abnormal, clinically significant” by the Investigator will be reported as AEs.

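### The tracer activity, volume, puff count and inhalation time do not agree between protocol sections, and 25 and 50 MBq serve as both limit and target

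*Protocol*

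**What the plan says.** **Volume and activity.** Section 11.3.4 has each Part A subject inhale, in each of two scans, "to receive about 10-24 µL solution corresponding to approximately 25 MBq". Section 6.1.2 gives the same volume range, puts it down to labelling yield that varies by batch, and describes filling the device to deliver 25 MBq. For Part B, section 11.3.5 has "to receive about 12 µL solution corresponding to approximately 50 MBq". Section 6.3 expects about 200 MBq in the device and does not separate the two parts.

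**Inhalations and puffs.**
- Section 6.1.2: 25 MBq from a single inhalation of 3-5 seconds.
- Section 6.3: about 25 MBq "by two 3-5 second inhalations, as 1-2 consecutive puffs withdrawn from the device for each tracer administration".
- Section 10.5: "Product use in the study sessions will consist of 1-2 puffs of each 3-5 seconds".
- Sections 11.3.4 and 11.3.5: 1-2 puffs, with about 3-5 seconds given for the inhaling.
- Section 8.1.2 (and the synopsis), Part B: "The subjects will have one PET-assessments each (PET 3) after two inhalations of" the tracer.

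**Limit or target.** Section 8.1.2 words the Part B activity as a maximum, "to obtain a tracer dose of up to 50 MBq", and section 8.1.1 does the same for 25 MBq per session in Part A. Sections 11.3.4 and 11.3.5 give the same two numbers as approximate amounts to be received. Section 6.3 combines both wordings for 25 MBq. Section 11.4.2.13 counts anything above the dose specified for the cohort as an overdose, and sends an overdose without symptoms to the medical records only.

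**The concern.** These are working instructions for the PET Centre and the subject, and they describe the exposure whose deposition is the primary outcome of Part A. If volume, activity and puff number cannot all be met with the one preparation described, staff must choose which to follow, and may choose differently from session to session. One puff or two, lasting 3 seconds in total or 10, is a different inhalation pattern. With 5 subjects per formulation in Part A and 2 in Part B, such differences will not average out.

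Part B is the more exposed. Section 17.5 already warns that the brain signal may be hard to measure, and the decision to add 3 subjects depends on quantifiable uptake. An activity well below the stated 50 MBq would weaken that reading.

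The limit/target question is separate. If the same number is both what is aimed at and what must not be exceeded, it is unclear which sessions count as overdoses.

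**Working it through.** **Inputs.** Part A: 10-24 µL for 25 MBq (6.1.2, 11.3.4). Part B: 12 µL for 50 MBq (11.3.5). Device content: 200 MBq (6.3). Pod: 1.5 mL, "which lasts approximately 200 puffs, depending on individual use behaviours" (6.1.1). Dose coefficient: 0.004 mSv/MBq; CT dose 0.28 mSv in Part A and 0.05 mSv in Part B (6.3).

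**Step 1, the protocol's own radiation figures.** 50 × 0.004 = 0.20 mSv, as stated. Part A: 0.20 + 0.28 = 0.48 mSv (stated 0.5). Part B: 0.20 + 0.05 = 0.25 mSv (stated 0.3). These reproduce.

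**Step 2, concentration = activity / volume.**
- Part A: 25/24 = 1.04 to 25/10 = 2.50 MBq/µL.
- Part B: 50/12 = 4.17 MBq/µL.
- Ratio: 4.17/2.50 = 1.7 to 4.17/1.04 = 4.0. Part B lies above the Part A range even at its most concentrated end.

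**Step 3, what the Part A range implies for Part B.**
- Activity in 12 µL: 12 × 1.04 = 12.5 to 12 × 2.50 = 30 MBq, or 25-60% of 50 MBq.
- Volume for 50 MBq: 50/2.50 = 20 to 50/1.04 = 48 µL. This is simply twice the Part A range, so reading Part B as two Part A administrations does not explain 12 µL.
- If, and only if, 12 µL were given at Part A concentrations and image noise were limited by counts, relative noise would rise by √(50/30) = 1.3 to √(50/12.5) = 2.0.

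**Step 4, could a Part B fill reach 4.17 MBq/µL?** With 200 MBq in the device, the fill is 200/4.17 = 48 µL, against 200/2.50 = 80 to 200/1.04 = 192 µL for Part A. It is possible, but not described.

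**Step 5, inhalation time for one administration.**

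| Section | Count | Total time |
|---|---|---|
| 6.1.2 | one inhalation | 3-5 s |
| 6.3 | two inhalations, also 1-2 puffs | 6-10 s if two |
| 10.5 | 1-2 puffs, 3-5 s each | 3-10 s |
| 11.3.4, 11.3.5 | 1-2 puffs | about 3-5 s as worded |
| 8.1.2 (Part B) | two inhalations | not given |

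**Step 6, plausibility check on puffs.** 1500 µL / 200 = 7.5 µL per puff in typical use, so 1-2 puffs hold 7.5-15 µL. In puffs, 10 µL is 1.3, 12 µL is 1.6 and 24 µL is 3.2. The Part B volume fits; the top of the Part A range does not.

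**The case against.** The strongest reply is that the protocol fixes no concentration. Section 6.1.2 has the radioactivity of the eluate measured and the volume follow from it, so a more concentrated Part B batch contradicts nothing. That stands: the gap is unexplained, not impossible. It also means the 12.5-30 MBq and noise figures describe what would happen only if a Part A concentration were applied to the Part B volume.

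Second, delivered activity is known. The device is measured before and after inhalation (11.3.4), section 17.5 uses that as an input and expresses lung deposition relative to it, and section 10.4 logs quantities used. This stands too and limits the effect on the primary results. It does not recover the number or length of puffs.

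Third, some of the wordings are compatible. Two inhalations lie within 1-2 puffs, and section 10.5 treats the puff and the later inhalation into the lungs as separate acts. That softens the difference between 8.1.2 and 11.3.5. It does not settle the internal mismatch in 6.3, its disagreement with the single inhalation in 6.1.2, or the per-puff against overall duration in 10.5 and 11.3.

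A reader might also infer that 12 µL conflicts with the puff count. By the protocol's own pod figures it does not (1.6 puffs). Those figures depend on user behaviour and come with no puff length, so they are a rough check only, for 24 µL as well.

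**Conclusion.** The administration figures need reconciling on three counts: a Part B volume/activity pair 1.7 to 4.0 times more concentrated than Part A with no preparation to explain it; differing inhalation counts and durations for one administration; and 25 and 50 MBq used as both limit and approximate target, which leaves the overdose definition without a threshold. The concentration result needs only the stated volumes and activities. The noise figure of 1.3-2.0 is conditional on Part A concentrations and count-limited noise.

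Three further inferences are not supported. That about half of the sessions would exceed the stated activity assumes delivery centred symmetrically on it, and the protocol gives no delivery distribution. That batch yield would make puffs differ by formulation is speculation, since no yield by formulation is given. And no radiation limit is in question: even a 20% overshoot gives 60 × 0.004 + 0.28 = 0.52 mSv in Part A and 60 × 0.004 + 0.05 = 0.29 mSv in Part B, both below 1 mSv.

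Severity is minor to moderate: more than clerical, because these are operative instructions for the exposure under study, but contained, because delivered MBq is measured.

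**What to change.** Reconcile sections 6.1.2, 6.3, 8.1, 10.5, 11.3.4, 11.3.5 and 11.4.2.13, with the matching synopsis text, so that activity, volume, puff number and duration agree within each part. If Part B uses a different preparation or fill, describe it. State whether the activity is a limit or a target, so that the overdose definition can be applied. No particular dose, volume or puff number is preferred here; that choice belongs to the sponsor and the PET Centre.

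In addition to the MBq already measured, record puff number and delivered volume for each session, and list them by formulation next to deposition and uptake. The cost is protocol wording and one eCRF line per session.

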11.4 Assessments related to secondary endpoints

11.4.1 *PET endpoints*

Refer to Section 11.3.

11.4.2 *Adverse events*

The Principal Investigator is responsible for ensuring that all medical staff involved in the study is familiar with the content of this section and the content of the CTC standard operating procedures (SOPs) regarding handling of AEs.

11.4.2.1 *Definition of adverse event*

An AE is defined as any untoward medical occurrence in a subject administered an IP and which does not necessarily have a causal relationship with this treatment. An AE can therefore be any unfavourable and unintended sign (including clinically significant abnormal values from relevant tests, such as clinical safety laboratory tests, ECGs, vital signs), symptom, or disease temporally associated with the use of an IP, whether or not considered related to the IP.

11.4.2.2 *Definition of serious adverse event*

An SAE is any AE which:

- results in death
- is life-threatening (this refers to a reaction in which the subject was at risk of death at the time of the reaction; it does not refer to a reaction that hypothetically might had led to death if the reaction was more severe)
- requires in-patient hospitalisation or prolongation of existing hospitalisation
- results in persistent or significant disability/incapacity
- is a congenital anomaly/birth defect
- is an important medical event (IME) (this refers to a reaction that may not be immediately life-threatening or result in death or hospitalisation, but may jeopardise the subject or may require intervention to prevent any of the other outcomes defined above)

Examples of IMEs are intensive treatment in an emergency room for allergic bronchospasm or blood dyscrasias, convulsions that do not result in hospitalisation, development of drug dependency, and drug abuse.

Planned hospitalisations or surgical interventions for a condition that existed before the subject signed the ICF and that did not change in intensity are not SAEs.

If there is any doubt as to whether an AE meets the definition of an SAE, a conservative viewpoint must be taken, and the AE must be reported as an SAE.

